## DOCUMENT HISTORY

Document	Date of Issue	Overall Rationale
Amendment 04	28-APR-2021	This amendment was issued to update the dose modification and toxicity management guidelines for irAEs.
Amendment 03	09-JAN-2019	This is a Canada-specific amendment to address Agency feedback.
Amendment 02	20-DEC-2018	This amendment was issued to address Agency feedback.
Amendment 01	19-OCT-2018	This amendment incorporates the approved Study Design (Figure 1).
Original protocol	12-OCT-2018	N/A

## PROTOCOL AMENDMENT SUMMARY OF CHANGES

**Amendment:** 04

### Overall Rationale for the Amendments:

This amendment was issued to update the dose modification and toxicity management guidelines for irAEs.

### Summary of Changes Table:

Section # and Name	Description of Change	Brief Rationale
6.6.1.2.1 Immune-Related Events and Dose Modification (Withhold, Treat, Discontinue)	The dose modification and toxicity management guidelines for irAEs and table were updated.	The dose modification and toxicity management guidelines for irAEs and table were updated as requested by the U.S. FDA in an effort to harmonize the presentation of safety information across all FDA-approved PD-1/L1 antibody prescribing information.

## 1 PROTOCOL SUMMARY

### 1.1 Synopsis

**Protocol Title:** A Phase 1b Multi-center Clinical Study of Selumetinib (MK-5618) in Combination with Pembrolizumab (MK-3475) in Participants with Advanced/Metastatic Solid Tumors.

**Short Title:** A Phase 1b Study of Selumetinib plus Pembrolizumab in Metastatic/Advanced Solid Tumors

**Acronym:**

**Hypotheses, Objectives, and Endpoints:**

There is no hypothesis testing in this study.

The objectives and endpoints apply to the study population of male and female participants at least 18 years of age with metastatic/advanced solid tumors. Participants receiving selumetinib in combination with pembrolizumab will be evaluated as follows:

Primary Objectives	Primary Endpoints
- To determine the safety and tolerability and to establish a preliminary recommended Phase 2 dose (RP2D) of selumetinib when used in combination with pembrolizumab	- Dose-limiting toxicities (DLTs) - Adverse events (AEs) - Study drug discontinuations due to an AE
Secondary Objectives	Secondary Endpoints
- To evaluate the pharmacokinetics (PK) of selumetinib	- Pharmacokinetic parameters including area under the curve (AUC), minimum concentration ( $C_{min}$ ) and maximum concentration ( $C_{max}$ )

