Duration of Participation	
Each participant will participate in the study from the time the participant signs the informed consent form (ICF) through the final protocol-specified contact.
 
After a screening phase of up to 28 days, each participant will be assigned to receive study treatment until disease progression is radiographically documented, confirmed by the site per modified Response Evaluation Criteria in Solid Tumors 1.1 for immune-based therapeutics (iRECIST) when clinically appropriate; unacceptable adverse event(s) (AEs); intercurrent illness that prevents further administration of treatment; investigator's decision to discontinue the participant; or administrative reasons requiring cessation of treatment; or until the participant has received 35 treatment cycles of selumetinib and pembrolizumab treatment (approximately 2 years). After the end of treatment, participants are to be followed up for safety for at least 30 days following the last study dosing and until recovery or stabilization of all related toxicities. During the first year in the study, tumor measurements will continue to be made every 9 weeks until progressive disease is observed, and each participant will be followed for survival. After 12 months on study, imaging will be performed every 12 weeks from first dose or as clinically indicated.
 
Participants who discontinue for reasons other than radiographic disease progression will have post-treatment follow-up imaging for disease status until disease progression is documented radiographically per RECIST 1.1 and when clinically appropriate, confirmed by the site per iRECIST (for participants treated with pembrolizumab), the start of a new anti-cancer treatment, withdrawal of consent, pregnancy, death, or loss to follow-up.
 
All participants will be followed by telephone for overall survival until death, withdrawal of consent, or the end of the study, whichever occurs first.
 
Upon identification of the preliminary RP2D of selumetinib for use in combination with pembrolizumab, additional participants with solid tumors will be enrolled in the dose expansion phase of this trial. Participants in the expansion phase of this trial will receive selumetinib in combination with pembrolizumab as dual therapy. The dose expansion phase in this study will be initiated through an amendment to this protocol.

---------------------------	---

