#### 4.2.1.2 Safety Endpoints

The primary safety endpoint is the incidence of DLTs and number of discontinuations of study treatment due to an AE. Safety and tolerability will be assessed by clinical review throughout the trial. The toxicities and grades experienced by participants who have received study treatment, including AEs, SAEs and events of clinical interest (ECIs) will be summarized. Other safety measures evaluated in study include laboratory tests, ECGs, echocardiogram (ECHO)/multigated acquisition (MUGA) scan, vital signs, ECG measurements, physical examinations, and eye examination.

[figure not shown]

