#### **8.4.1 Time Period and Frequency for Collecting AE, SAE, and Other Reportable Safety Event Information**

All AEs, SAEs, and other reportable safety events that occur after the consent form is signed but before intervention allocation/randomization must be reported by the investigator if the participant is receiving placebo run-in or other run-in treatment, if the event cause the participant to be excluded from the study, or is the result of a protocol-specified intervention, including but not limited to washout or discontinuation of usual therapy, diet, or a procedure.

- All AEs from the time of intervention allocation/randomization through 30 days following cessation of study intervention must be reported by the investigator.
- All AEs meeting serious criteria, from the time of intervention allocation/randomization through 90 days following cessation of study intervention or 30 days following cessation of study intervention if the participant initiates new anticancer therapy, whichever is earlier, must be reported by the investigator.
- All pregnancies and exposure during breastfeeding, from the time of intervention allocation/randomization through 120 days following cessation of study intervention, or 30 days following cessation of study intervention if the participant initiates new anticancer therapy must be reported by the investigator.
- Additionally, any SAE brought to the attention of an investigator at any time outside of the time period specified above must be reported immediately to the Sponsor if the event is considered drug-related.

Investigators are not obligated to actively seek AEs or SAEs or other reportable safety events in former study participants. However, if the investigator learns of any SAE, including a death, at any time after a participant has been discharged from the study, and he/she considers the event to be reasonably related to the study intervention or study participation, the investigator must promptly notify the Sponsor.

All initial and follow-up AEs, SAEs, and other reportable safety events will be recorded and reported to the Sponsor or designee within the time frames as indicated in [Table 8](#).

Table 8 Reporting Time Periods and Time Frames for Adverse Events and Other Reportable Safety Events

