### **9.6.2 Statistical Methods for Safety Analysis**

Safety and tolerability will be assessed by clinical review of all relevant parameters including AEs, SAEs, laboratory tests, vital signs, ECG measurements, and physical examinations.

Adverse events will be summarized by counts and frequencies for each dose level. Laboratory tests, vital signs, and other safety endpoints will be summarized.

Dose limiting toxicities will be listed and summarized by dose level. The isotonic regression with pool-adjacent-violators-algorithm [Ji Y, Li Y, Bekele BN 2007], which forces the DLT rate estimates to be nondecreasing with increasing dose levels and pools adjacent violators for weighted estimates by sample size, will be used to estimate the DLT rates across doses in each treatment arm. The estimate of the DLT rate among participants treated at the RP2D and the 80% Bayesian credible interval based on a prior distribution of Beta (1,1) for the estimate will be provided.

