### **9.7 Interim Analyses**

An interim analysis may be conducted to enable future trial planning at the Sponsor's discretion and data will be examined on a continuous basis to allow for dose finding decisions.

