### **9.12 Extent of Exposure**

The extent of exposure will be summarized as duration of treatment in cycles.

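### Section 9.6.2 summarizes AEs by dose level as crude counts and gives AE discontinuations no method of their own, so at the RP2D decision the most recently filled level can look better than it is

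*Combined protocol and SAP*

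**What the plan says.** The primary objective in Sections 1.1 and 3 covers safety, tolerability and a preliminary RP2D. Besides DLTs its endpoints are "Adverse events (AEs) - Study drug discontinuations due to an AE". Section 4.2.1.2 expresses the last of these as the "number of discontinuations of study treatment due to an AE".

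The analysis in Section 9.6.2 is brief. For AEs: "Adverse events will be summarized by counts and frequencies for each dose level". Discontinuations due to an AE are not named there and can only fall under the next sentence: "Laboratory tests, vital signs, and other safety endpoints will be summarized". Section 9.12 adds "The extent of exposure will be summarized as duration of treatment in cycles", without saying that this is done by dose level or that it serves as a denominator.

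Time at risk differs between participants. Section 8.4.1 sets the collection period: "All AEs from the time of intervention allocation/randomization through 30 days following cessation of study intervention must be reported by the investigator". Treatment may continue "until the participant has received 35 treatment cycles of selumetinib and pembrolizumab treatment (approximately 2 years". Only DLTs have a common window, 21 days (Sections 4.3.1.4 and 6.6.2.2).

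The Synopsis describes the intervention model as sequential. Sections 4.1 and 4.3.1.4 say that the dose or doses to carry forward will be decided on the totality of the data, and Section 9.7 says that "data will be examined on a continuous basis to allow for dose finding decisions". No data cut or minimum follow-up per level is given for the RP2D decision.

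**The concern.** A crude proportion with an event depends on both the event rate and how long people were watched. In a sequential escalation, the levels opened first have been watched longest when the dose is chosen. A by-dose table of crude frequencies produced at that moment therefore mixes dose with order of entry.

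This matters because these two endpoints are the ones that can show intolerance after Cycle 1, which the 21-day DLT rule cannot see. Section 6.6.1.2.1 itself notes that immune-related events can appear months after the last pembrolizumab dose. If later-cycle toxicity is understated at the level being considered, the tolerability part of the primary objective is answered too favourably, and the expansion phase starts from that dose. Complete AE collection would not cure this, because the cause is unequal time on treatment.

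**Working it through.** **1. The plan's own figure.** 35 cycles x 21 days = 735 days = 105 weeks, about 24.1 months. This agrees with the stated two years or so, and is the range over which time at risk can vary. The documents give no AE rate, drop-off rate or expected exposure by level, so what follows rests on assumptions.

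**2. Assumptions.** AE-discontinuation hazard h = 3% per cycle at the lowest doses and 6% at the newest level; stopping for other reasons g = 10%, 15% or 20% per cycle. For potential follow-up when dose finding ends, a simulation of the Table 1 rule was used (cohorts of 3-6, enrolment over 7-14 days, 21-day DLT window, assumed true MTD at DL5). It gave a median of 13 cycles at DL1-DL2 and 4 at the top-filled dose.

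**3. Formula.** With n potential cycles, crude proportion = h/(h+g) x [1 - (1-h-g)^n].

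**4. Worked case, g = 15%.**
- Lowest doses, n = 13: 0.03/0.18 x (1 - 0.82^13) = 0.1667 x 0.924 = 15.4%.
- Newest level with no dose effect, n = 4: 0.1667 x (1 - 0.82^4) = 9.1%. Shorter follow-up alone makes it look better.
- Newest level with doubled hazard, n = 4: 0.06/0.21 x (1 - 0.79^4) = 0.2857 x 0.6105 = 17.4%. A true ratio of 2 appears as 17.4/15.4 = 1.13.
- First two cycles only: 0.03 x (1 + 0.82) = 5.5% against 0.06 x (1 + 0.79) = 10.7%, a ratio of 1.97.

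**5. Range over drop-off.**

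| g | Lowest doses, 13 cycles | Newest level, doubled hazard, 4 cycles | Crude ratio at early cut | Crude ratio when all could have 35 cycles |
|---|---|---|---|---|
| 10% | 19.3% | 18.8% | 0.98 | 37.4/22.9 = 1.63 |
| 15% | 15.4% | 17.4% | 1.13 | 28.6/16.7 = 1.72 |
| 20% | 12.6% | 16.2% | 1.28 | 23.1/13.0 = 1.77 |

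The simulation lets follow-up vary between participants, and gave (newest level against lowest doses) 17.7% v 18.8%, 15.8% v 15.4% and 14.6% v 12.5% for the same three values of g.

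**6. A second model in calendar time.** Hazards of 0.05 and 0.10 per month, median 3 months to stopping for other reasons, levels 2 months apart, 8 participants at the two lowest levels together and 14 at the last. At the dose-selection cut, crude proportions are 16.8% (lowest) and 12.8% (selected) despite the doubled hazard, with mean exposure of 3.4 and 1.3 months. The selected dose looks no worse in 58% of runs (49-72% over medians of 2-6 months and spacings of 1.5-2.4 months). With events per person-month this falls to 31% (29-36%). When everyone could complete 35 cycles the crude figures are 18% and 30%.

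**The case against.** The strongest reply is that Section 9.6.2 plans no comparison. Section 9.3 says there is no hypothesis testing, AEs are to be summarized, and safety is assessed by clinical review of all relevant parameters. The preliminary MTD comes from isotonic DLT rates on a fixed window. An open-label team looking at participant-level data continuously will know who has had four cycles and who thirteen, and Section 9.12 shows exposure. All of this is correct. A reader might infer that the plan compares doses on crude counts, or that the RP2D is set by them; the documents say neither. What remains is that a by-dose table of primary endpoints feeding a dose decision will be read across doses, and nothing in the primary-objective methods puts the levels on a common footing. The supplemental SAP does not fill the gap, because Section 9.1 reserves it for exploratory and other nonconfirmatory analyses.

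Two other tempting readings also fail. One is that the distortion always favours higher doses. Section 4.3.1.4 allows up to 14 new participants at a lower dose after a D or DU decision, so the least-followed level can be a lower one. The other is that the final tables are equally affected. The study is planned for about 40 months, and 24.1 months of treatment plus 30 days of follow-up leave roughly 14-15 months for accrual, so at study end every level can have had 35 cycles.

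Small numbers also limit the gain. With 8 and 14 participants and the simulation's two-cycle proportions of 5.5% and 10.8%, the newest level looks worse in 65% of trials, equal in 13% and better in 23% (rounded). With crude proportions of 15.4% and 15.8% it looks worse in 54%. A common window improves the reading by about 11 percentage points and does not settle it.

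**Conclusion.** The point holds for the RP2D decision and any interim look. Two primary endpoints with variable time at risk have only crude or unspecified summaries by dose level, so the most recently filled level can appear better tolerated than it is. Under the assumptions in the working, a doubled AE-discontinuation hazard shows as a crude ratio of about 1.0 to 1.3 at that cut and 1.6 to 1.8 at a mature one. The closed form hides the doubling completely when the newest level has about 2.6 to 4.2 potential cycles against 13.

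The doubling, the constant hazards, the drop-off rates and the entry pattern are illustrations and do not come from the documents; only the mechanism does. This is an inexpensive improvement to a descriptive analysis. It does not show that the DLT-based dose finding or the final safety tables are invalid.

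**What to change.** In Section 9.6.2 keep the overall counts and add, by dose level, for AEs, Grade 3 or higher AEs and discontinuations due to an AE:

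- incidence within common early windows from first dose (Cycle 1; Cycles 1-2), with cumulative incidence treating other reasons for stopping as competing events for longer windows. Restricting a Cycles 1-4 table to participants with full potential follow-up could drop up to about half of the newest level, so cumulative incidence is preferable there;
- first events per 100 participant-cycles on treatment.

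Report exposure in cycles by dose level next to these. State the data cut and the follow-up available per level for the RP2D review, so that the review reads these summaries beside the crude frequencies.

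The cost is a paragraph and a few descriptive tables from data already collected, with no added visits or participants and no change to any dosing rule. With 3-14 participants per level the estimates will be imprecise, and the rates per participant-cycle assume a roughly constant hazard.

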### Overall Design:

Study Phase	Phase 1
Primary Purpose	Treatment
Indication	Advanced Metastatic Solid Tumors
Population	Participants with advanced metastatic solid tumors
Study Type	Interventional
Intervention Model	Sequential This is a multi-site study.
Type of Control	No treatment control
Study Blinding	Unblinded Open-label
Masking	No Masking
Estimated Duration of Study	The Sponsor estimates that the study will require approximately 40 months from the time the first participant signs the informed consent until the last participant's last study-related telephone call or visit.

### Number of Participants:

Approximately 50 participants will be enrolled in this dose escalation study, as described in Section 9; the overall sample size will be 84 participants maximum for this dose escalation study.

**Intervention Groups and Duration:**

Intervention Groups	This is a multiple dose escalation study using the single agent, modified toxicity probability interval (mTPI) design and will evaluate safety, tolerability, and efficacy in the following treatment interventions:							
Intervention Group Name	Drug	Dose Level	Dose Strength	Dose Frequency	Route of Admin.	Regimen/ Treatment Period/ Vaccination Regimen	Use	
Selumetinib	MK-5618	DL 1	50 mg	BID	Oral	2 weeks on followed by 1 week off	Experimental	
	MK-5618	DL 2	75 mg	BID	Oral	2 weeks on followed by 1 week off	Experimental	
	MK-5618	DL3	100 mg	BID	Oral	2 weeks on followed by 1 week off	Experimental	
	MK-5618	DL4	125 mg	BID	Oral	2 weeks on followed by 1 week off	Experimental	
	MK-5618	DL5	150 mg	BID	Oral	2 weeks on followed by 1 week off	Experimental	
	MK-5618	DL6	200 mg	BID	Oral	2 weeks on followed by 1 week off	Experimental	
	MK-5618	DL7 onwards	Above 200 mg (up to 300 mg)	BID	Oral	2 weeks on followed by 1 week off	Experimental	
Pembrolizumab	MK-3475	DL1-DL7	200 mg	Once every 3 weeks	IV Infusion	Every 3 weeks (Q3W)	Experimental	
Abbreviations: BID = twice daily; IV = intravenous								
Total Number	Based on the emerging safety and/or efficacy signals, an alternate dose level, alternative drug administration frequency and dosing schedule(s) may be explored and an optimal dose will be selected based on totality of data (PK, PD and safety) emerging throughout the trial.							
	There is 1 intervention group (selumetinib + pembrolizumab) in this dose escalation study.							

Duration of Participation	
Each participant will participate in the study from the time the participant signs the informed consent form (ICF) through the final protocol-specified contact.
 
After a screening phase of up to 28 days, each participant will be assigned to receive study treatment until disease progression is radiographically documented, confirmed by the site per modified Response Evaluation Criteria in Solid Tumors 1.1 for immune-based therapeutics (iRECIST) when clinically appropriate; unacceptable adverse event(s) (AEs); intercurrent illness that prevents further administration of treatment; investigator's decision to discontinue the participant; or administrative reasons requiring cessation of treatment; or until the participant has received 35 treatment cycles of selumetinib and pembrolizumab treatment (approximately 2 years). After the end of treatment, participants are to be followed up for safety for at least 30 days following the last study dosing and until recovery or stabilization of all related toxicities. During the first year in the study, tumor measurements will continue to be made every 9 weeks until progressive disease is observed, and each participant will be followed for survival. After 12 months on study, imaging will be performed every 12 weeks from first dose or as clinically indicated.
 
Participants who discontinue for reasons other than radiographic disease progression will have post-treatment follow-up imaging for disease status until disease progression is documented radiographically per RECIST 1.1 and when clinically appropriate, confirmed by the site per iRECIST (for participants treated with pembrolizumab), the start of a new anti-cancer treatment, withdrawal of consent, pregnancy, death, or loss to follow-up.
 
All participants will be followed by telephone for overall survival until death, withdrawal of consent, or the end of the study, whichever occurs first.
 
Upon identification of the preliminary RP2D of selumetinib for use in combination with pembrolizumab, additional participants with solid tumors will be enrolled in the dose expansion phase of this trial. Participants in the expansion phase of this trial will receive selumetinib in combination with pembrolizumab as dual therapy. The dose expansion phase in this study will be initiated through an amendment to this protocol.

---------------------------	---

## Study Governance Committees:

Steering Committee	No
Executive Oversight Committee	No
Data Monitoring Committee	No
Clinical Adjudication Committee	No
Insert Other Oversight Committee	No
Study governance considerations are outlined in Appendix 1.	

## Study Accepts Healthy Volunteers: No

A list of abbreviations used in this document can be found in Appendix 8.

### 1.2 Schema

[figure not shown]

Figure 1 Study Design: Dose Escalation of Selumetinib in Combination with Pembrolizumab

### 1.3 Schedule of Activities (SoA)

#### Dose Escalation

Study Period:	Screening Phase	Treatment Cycles (3-week Cycles)										End of Treatment (EoT)	Post-treatment			Notes
		1	2	3	4	5		6	7	8 to 35	Discontinuation	Safety Follow-up	Follow-up Visits	Survival Follow-up		
Treatment Cycle (C) / Visit:	Screening (Visit 1)									At time of Treatment Discontinuation	30 days Post-last dose	Q9W or Q12W Post-discon	Every 12 weeks Post-discon			
Scheduling Window (Days)	-28 to -1		±3	-3	±3	±3	±3	-3	±3	±3	±3	±7	±7	±14		

